1.3 Nivolumab Background and Associated Known Toxicities

Nivolumab (also referred to as BMS-936558 or MDX1106) is a human monoclonal antibody (HuMAb; immunoglobulin G4 [IgG4]-S228P) that targets the programmed death-1 (PD-1) cluster of differentiation 279 (CD279) cell surface membrane receptor. PD-1 is a negative regulatory molecule expressed by activated T and B lymphocytes³⁴. Binding of PD-1 to its ligands, programmed death-ligands 1 (PD-L1) and 2 (PD-L2),

results in the down-regulation of lymphocyte activation. Inhibition of the interaction between PD-1 and its ligands promotes immune responses and antigen-specific T-cell responses to both foreign antigens as well as self-antigens. Nivolumab is expressed in Chinese hamster ovary (CHO) cells and is produced using standard mammalian cell cultivation and chromatographic purification technologies. The clinical study product is a sterile solution for parenteral administration. OPDIVO™ (nivolumab) is approved for use in multiple countries including the United States (US, Dec-2014), the European Union (EU, Jun-2015), and Japan (Jul-2014).

1.31 Nonclinical Studies

Nivolumab has been shown to bind specifically to the human PD-1 receptor and not to related members of the CD28 family.^{2,3} Nivolumab inhibits the interaction of PD-1 with its ligands, PD-L1 and PD-L2, resulting in enhanced T-cell proliferation and interferon-gamma (IFN- γ) release in vitro.^{4,5,6} Nivolumab binds with high affinity to activated human T-cells expressing cell surface PD-1 and to cynomolgus monkey PD-1.² In a mixed lymphocyte reaction (MLR), nivolumab promoted a reproducible concentration-dependent enhancement of IFN- γ release³⁵.

In intravenous (IV) repeat-dose toxicology studies in cynomolgus monkeys, nivolumab was well tolerated at doses up to 50 mg/kg, administered weekly for 5 weeks, and at doses up to 50 mg/kg, administered twice weekly for 27 doses. While nivolumab alone was well tolerated in cynomolgus monkeys, combination studies have highlighted the potential for enhanced toxicity when combined with other immunostimulatory agents³⁶.

In addition, an enhanced pre- and postnatal development (ePPND) study in pregnant cynomolgus monkeys with nivolumab was conducted³⁷. Administration of nivolumab at up to 50 mg/kg 2QW was well tolerated by pregnant monkeys; however, nivolumab was determined to be a selective developmental toxicant when administered from the period of organogenesis to parturition at ≥ 10 mg/kg (area under the concentration-time curve [AUC] from time zero to 168 hours [AUC(0-168 h)] 117,000 $\mu\text{g}\cdot\text{h}/\text{mL}$). Specifically, increased developmental mortality (including late gestational fetal losses and extreme prematurity with associated neonatal mortality) was noted in the absence of overt maternal toxicity. There were no nivolumab-related changes in surviving infants tested throughout the 6-month postnatal period. Although the cause of these pregnancy failures was undetermined, nivolumab-related effects on pregnancy maintenance are consistent with the established role of PD-L1 in maintaining fetomaternal tolerance in mice³⁸. Approved v 15.0 930038243 16.0 18 Investigator Brochure^{SEP} BMS-936558/MDX1106 nivolumab.

1.32 Effects in Humans

The PK, clinical activity, and safety of nivolumab have been assessed in subjects with non-small cell lung cancer (NSCLC), melanoma, and clear-cell renal cell carcinoma (RCC) in addition to other tumor types. Clinical activity and safety information presented in this Investigator Brochure (IB) focuses primarily on that obtained from Phase 2/3 studies (CA209063, CA209017, CA209057, ONO-4538-05, and ONO-4538-06) in subjects with advanced or metastatic squamous (SQ) and nonsquamous (NSQ) NSCLC, Phase 2/3 studies (CA209037, CA209066, CA209067, and CA209069) in subjects with unresectable or metastatic melanoma, and a Phase 2 study (CA209010) in subjects with advanced

or metastatic clear-cell RCC. Data are also provided from Phase 1 studies MDX1106-03, CA209012, CA209016, and CA209039 and from Phase 1 safety cohort of CA209143. Nivolumab is being investigated both as monotherapy and in combination with chemotherapy, targeted therapies, and other immunotherapies.

Nivolumab is approved in multiple countries including the US for treatment of previously treated, unresectable or metastatic melanoma and previously treated, metastatic squamous NSCLC, the EU for treatment of previously treated, unresectable or metastatic melanoma, and Japan for treatment of unresectable melanoma.

1.33 Clinical Pharmacokinetics

The pharmacokinetics (PK) of nivolumab was studied in subjects over a dose range of 0.1 to 10 mg/kg administered as a single dose or as multiple doses of nivolumab every 2 or 3 weeks. The geometric mean (% CV%) clearance (CL) was 9.5 mL/h (49.7%), geometric mean volume of distribution at steady state (V_{ss}) was 8.0 L (30.4%), and geometric mean elimination half-life (t_{1/2}) was 26.7 days (101%). Steady-state concentrations of nivolumab were reached by 12 weeks when administered at 3 mg/kg Q2W, and systemic accumulation was approximately 3-fold. The exposure to nivolumab increased dose proportionally over the dose range of 0.1 to 10 mg/kg administered every 2 weeks. The clearance of nivolumab increased with increasing body weight. The PPK analysis suggested that the following factors had no clinically important effect on the CL of nivolumab: age (29 to 87 years), gender, race, baseline LDH, PD-L1. A PPK analysis suggested no difference in CL of nivolumab based on age, gender, race, tumor type, baseline tumor size, and hepatic impairment.

Although ECOG status, baseline glomerular filtration rate (GFR), albumin, body weight, and mild hepatic impairment had an effect on nivolumab CL, the effect was not clinically meaningful. When nivolumab is administered in combination with ipilimumab, the CL of nivolumab was increased by 24%, whereas there was no effect on the clearance of ipilimumab. Additionally, PPK and exposure response analyses have been performed to support use of 240 mg Q2W dosing in addition to the 3 mg/kg Q2W regimen. Using the PPK model, exposure of nivolumab at 240 mg flat dose was identical to a dose of 3 mg/kg for subjects weighing 80 kg, which was the approximate median body weight in nivolumab clinical trials.

1.34 Clinical Efficacy

Nivolumab has demonstrated durable responses exceeding 6 months as monotherapy and in combination with ipilimumab or other agents in several tumor types, including NSCLC, melanoma, RCC, and some lymphomas^{9,11,39}. In confirmatory trials, nivolumab as monotherapy demonstrated a statistically significant improvement in OS as compared with the current standard of care in subjects with advanced or metastatic NSCLC and in subjects with unresectable or metastatic melanoma. Nivolumab in combination with ipilimumab improved PFS and ORR over ipilimumab alone in subjects with unresectable or metastatic melanoma.

1.4 Safety in Subjects with Relapsed or Refractory Hematologic Malignancies

CA209039 Nivolumab, at 1 or 3 mg/kg, has an acceptable safety profile in subjects with relapsed or refractory hematologic malignancy, as demonstrated by the frequency, severity, and types of AEs, drug-related deaths, SAEs, and AEs leading to

discontinuation. The following were the key safety findings for 105 subjects treated with nivolumab monotherapy in CA209039 as of 15-Apr-2015:

- The most frequently reported drug-related AEs (> 10% of subjects) were fatigue (16.2%) and rash (10.5%). The majority were Grade 1-2 in severity.
- The most frequently reported drug-related SAE was pneumonitis (4.8%).
- Drug-related AEs leading to discontinuation were reported for 14.3% of subjects. The most frequently reported AE leading to discontinuation were pneumonitis (2.9%).
- The most frequently reported drug-related select AE categories were skin (19.0%), GI (9.5%), and pulmonary (9.5%). The most frequently reported ($\geq 5\%$ of total treated subjects) drug-related select AEs were rash (10.5%), pneumonitis (9.5%), pruritus (9.5%), and diarrhea (8.6%). Drug-related select AEs were mostly Grade 1-2 in all categories.
- Most deaths were due to disease progression. One death was reported due to study drug toxicity (The subject with non Hodgkin's lymphoma [small lymphocytic lymphoma] in the 3 mg/kg treatment group died due to Grade 5 pneumonitis with onset 10 days after the subject received the only dose of nivolumab).

1.41 Clinical Activity of Nivolumab in Lymphoma

In a broad phase II study, Ansell et al treated 23 patients with classical HL who had been heavily pretreated⁹. Nivolumab at a dose of 3 mg/kg was administered q 2 weeks until CR < tumor progression, or toxicity. Of these, 78% had progressed following a prior autologous stem cell transplant, and 78% following brentuximab vedotin. An objective response was achieved in 87%, including 17% with a CR. The rate of progression-free survival at 24 weeks was 86%. Therapy was discontinued in 6 patients to go to stem cell transplantation, with disease progression in 4, and toxicity in 2.

From the same study Lesokhin et al reported 29 patients with a variety of histologies of B-NHL with responses in 36% of diffuse large B-cell NHL (9% CR), 40% of follicular NHL (10% CR)⁴⁰.

1.5 Rationale

Given the impressive activity of both Brentuximab Vedotin and nivolumab in patients with relapsed and refractory Hodgkin Lymphoma, and their lack of overlapping toxicities, the combination is worthy of study. Given the poor results and tolerability of traditional chemotherapy in older patients with Hodgkin Lymphoma, as described above, this combination can be considered for first-line therapy.

2.0 Goals

2.1 Primary

2.11 The primary objective of the study is to determine the efficacy based on overall metabolic response rate (PMR + CMR) of Brentuximab Vedotin /Nivolumab in previously untreated Hodgkin Lymphoma patients 60 years of age or older, or those considered unsuitable for standard chemotherapy because of a low cardiac ejection fraction (<50%) or impaired pulmonary or renal function.

2.2 Secondary

2.21 The complete metabolic response (CMR) rate

2.22 Safety and tolerability of the regimen in this patient population

2.23 Duration of response (DOR)

2.24 Progression-free survival (PFS)

2.25 Overall survival (OS)

2.3 Correlative Research

2.31 T-cell/cytokine– peripheral blood specimens will be used to assess T-cell activation and cytokine up regulation as measures of treatment effect. This goal will be exploratory in nature and reported descriptively.

2.32 Biomarkers- intratumoral cell populations, genetic variability, serum cytokines and T-cell activation will be evaluated to identify potential biomarkers that correlate with response to therapy. This goal will also be exploratory in nature.

3.0 Patient Eligibility

Prior to discussing protocol entry with the patient, call the [REDACTED] for dose level and to ensure that a place on the protocol is open to the patient.

3.1 Registration – Inclusion Criteria

3.11 Classical Hodgkin Lymphoma determined by local hematopathology review

3.12 One of the following:

- Age \geq 60 years
- Age <60 years but unsuitable for standard chemotherapy because of a cardiac ejection fraction of <50%, a pulmonary diffusion capacity <80%, or a creatinine clearance \geq 30 and <60 mL/min, or refused standard chemotherapy despite efforts to convince them otherwise.

Cockcroft-Gault Equation:

$$\text{Creatinine clearance for males} = \frac{(140 - \text{age})(\text{weight in kg})}{(72)(\text{serum creatinine in mg/dL})}$$

$$\text{Creatinine clearance for females} = \frac{(140 - \text{age})(\text{weight in kg})(0.85)}{(72)(\text{serum creatinine in mg/dL})}$$

- 3.13 Requirement for systemic chemotherapy: all stages except IA (not bulky disease), if involved field is considered Radiotherapy (RT) curative.
- 3.14 Previously untreated with either chemotherapy, radiation therapy or either brentuximab vedotin or nivolumab, or another check point inhibitor.
- 3.15 ECOG Performance Status (PS) 0, 1, or 2 (Appendix II)
- 3.16 The following laboratory values obtained ≤ 7 days prior to registration.
- Absolute neutrophil count (ANC) $\geq 1500/\text{mm}^3$, unless secondary to bone marrow involvement.
 - Leukocytes $\geq 3,000/\text{mm}^3$
 - Platelet count $\geq 100,000/\text{mm}^3$
 - Hemoglobin >9.0 g/dL – unless determined by treating physician to be disease related
 - Total bilirubin ≤ 1.5 x upper limit of normal (ULN)
 - Aspartate transaminase (AST) ≤ 2.5 x ULN
 - Alanine Transaminase (ALT) ≤ 2.5 x ULN
 - Creatinine ≤ 2.0 mg/dL
 - Amylase and/or lipase ≤ 1.5 x ULN
- 3.17 Women of childbearing potential must have a negative serum or urine pregnancy test (minimum sensitivity 25 IU/L or equivalent units of HCG) within 24 hours prior to registration
- Note: Women of child-bearing potential (WOCBP) must use appropriate method(s) of contraception. WOCBP should use an adequate method to avoid pregnancy for 23 weeks (30 days plus the time required for nivolumab to undergo five half-lives) after the last dose of investigational drug. Men who are sexually active with WOCBP must use any contraceptive method with a failure rate of less than 1% per year. Men receiving nivolumab and who are sexually active with WOCBP will be instructed to adhere to contraception for a period of 31 weeks after the last dose of investigational product. Women who are not of childbearing potential (ie, who are postmenopausal or surgically sterile) as well as azoospermic men do not require contraception. Should a woman become pregnant or suspect she is pregnant while participating in this study, she should inform her treating physician immediately.
- 3.18 Willing to return to enrolling institution for follow-up (during the Active Monitoring Phase of the study).
- Note: During the **Active Monitoring** Phase of a study (i.e., active treatment and observation), participants must be willing to return to the consenting institution for follow-up.*
- 3.19a Ability to understand and willingness to sign an informed written consent.

3.19b Provide blood and tissue samples for mandatory correlative research purposes (see sections 4.0, 14.0 and 17.0).

3.2.1 Registration – Exclusion Criteria

3.21 Any of the following because this study involves an investigational agent whose genotoxic, mutagenic and teratogenic effects on the developing fetus and newborn are unknown:

- Pregnant women
- Nursing women
- Men or women of childbearing potential who are unwilling to employ adequate contraception

3.22 Co-morbid systemic illnesses or other severe concurrent disease which, in the judgment of the investigator, would make the patient inappropriate for entry into this study or interfere significantly with the proper assessment of safety and toxicity of the prescribed regimens.

3.23 Active, known or suspected autoimmune disease. Note: Subjects are permitted to enroll if they have vitiligo, type I diabetes mellitus, residual hypothyroidism due to autoimmune condition only requiring hormone replacement, psoriasis not requiring systemic treatment, or conditions not expected to recur in the absence of an external trigger

3.24 Use of systemic treatment with either corticosteroids (> 10 mg daily prednisone equivalents) or other immunosuppressive medications ≤ 14 days of registration. Note: Inhaled or topical steroids and adrenal replacement doses > 10 mg daily prednisone equivalents are permitted in the absence of active autoimmune disease.

3.25 Immunocompromised patients, patients with known history of testing positive for human immunodeficiency virus (HIV) or known acquired immunodeficiency syndrome (AIDS) and currently receiving antiretroviral therapy, patients with a prior history of known or suspected autoimmune disease, active Hepatitis B virus surface antigen (HBV sAg+), active Hepatitis C (if Ab+ then PCR+) indicating acute or chronic infection, and/or history of interstitial lung disease.

3.26 Allergy to Brentuximab Vedotin and/or Nivolumab

3.27 Uncontrolled intercurrent illness including, but not limited to, ongoing or active infection, symptomatic congestive heart failure, unstable angina pectoris, cardiac arrhythmia, or psychiatric illness/social situations that would limit compliance with study requirements.

3.28 Receiving any other investigational agent which would be considered as a treatment for the primary neoplasm.

3.29a Have had prior chemotherapy or radiotherapy for Hodgkin lymphoma

3.29b Have received either of the study drugs

3.29c <60 years who are considered candidates for standard chemotherapy

- 3.29d \geq Grade 2 peripheral neuropathy
- 3.29e Other active malignancy \leq 2 years prior to registration, unless treated with curative intent. EXCEPTIONS: Non-melanotic skin cancer or carcinoma-in-situ of the cervix. NOTE: If there is a history or prior malignancy, they must not be receiving other specific treatment for their cancer.
- 3.29f Active CNS involvement or leptomeningeal metastases involvement.
- 3.29g Known history of pancreatitis.

4.0 Test Schedule

Tests and procedures	Active Monitoring Phase				
	Baseline <14 days of Registration	Prior to each new cycle ¹⁰ <= 3 days (starting at cycle 2)	Restaging End of Cycle 8 (6-8 Weeks after Day 1 of Cycle 8)	End of Treatment if discontinued early (at PD or PMD, withdrawal, or removal)	Observation (Every 30 days x 90 days, , then every 90 days x 2.5 years, then every 6 months until 5 years from registration) +/-14Days
History and exam	X	X ¹	X	X	X
B Symptoms ⁹	X	X	X	X	X
ECOG PS	X	X	X	X	X
Height (baseline only), Weight	X	X	X	X	X
Adverse event assessment	X	X	X	X	X
Cardiac ejection fraction	X ¹⁴				
ECG	X				
Pulmonary function studies (including oxygen saturation) ¹²	X				
HBV sAg and HCV Ab or HCV RNA	X				
Comprehensive metabolic panel: (ALT, AST, total bilirubin, alkaline phosphatase), BUN or serum urea level, creatinine, Ca, Mg, Na, K, Cl, LDH, Glucose, amylase, lipase, Albumin, bicarbonate	X ⁴	X	X	X	
INR ^{K, 13}		X	X	X	X
TSH (with Free T4 and Free T3)	X ⁴	X ¹¹	X	X	
Hematology: CBC/differential	X ⁴	X	X	X	X
Erythrocyte sedimentation rate	X				
Uric Acid	X				
Pregnancy Test ³	X	X	X	X	X
PET-CT	X ¹⁴	X ²	X	X	
CT scan Chest/Abd/Pelvis					X ⁵
Mandatory Research blood samples (See section 14.0) ^{K, 6}		X ¹⁵	X	X	X ⁸
Mandatory Tissue sample ^{7, K}	X				

(Footnotes on next page)

- 1 If on physical exam there are any palpable lymph nodes present: Tumor (bidimensional)-measurements by physical exam to be done at end of every cycle, prior to next cycle.
- 2 End of cycle 2, prior to Cycle 3 (≤ 5 days)
- 3 For women of childbearing potential only. A serum or urine pregnancy testing is required ≤ 24 hours before registration, then every other cycle. (more frequently if required by local standard). After discontinuation from nivolumab, these should be repeated at approximately 30 days and approximately 70 days [or more frequently if required by local standard].
- 4 Must be obtained ≤ 7 days prior to registration.
- 5 CT scan is every 3 months during the first year of observation, then as clinically indicated.
- 6 Must be drawn on Day 1 of each cycle before treatment Cycles 1-8, at restaging 6-8 weeks post Cycle 8 Day 1, end of treatment if discontinued early (PD or PMD, withdrawal or removal), and at time of PD or PMD.
- 7 To be submitted within ≤ 14 days following Registration; see 17.0 Pathology Considerations/Tissue Biospecimens
- 8 Only at time of PD or PMD
- 9 Unexplained persistent fever $> 38^{\circ}\text{C}$ (or $> 100.4^{\circ}\text{F}$) in previous month, recurring drenching night sweats during the previous month, and/or unexplained weight loss $> 10\%$ of body weight in the previous six months
- 10 If tests have been done ≤ 14 days prior to registration they need not be repeated for the first cycle.
- 11 Thyroid function testing should be done every third cycle day 1 (≤ 3 days) for subjects receiving nivolumab.
- 12 Oxygen saturation by pulse oximetry at rest (also specify supplemental oxygen level, if applicable) should be assessed at baseline
- 13 ONLY if clinically indicated
- 14 Must be obtained ≤ 28 days prior to registration.
- 15 Research blood draw to be done prior to every cycle, including Cycle 1.
- R Research funded (see Section 19.1)

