10.54 Baseline and Adverse Events Evaluations

Pre-treatment symptoms/conditions to be graded at baseline and adverse events to be graded at each evaluation per the CTCAE v4.0 grading unless otherwise stated in the table below:

System Organ Class	Adverse event/Symptoms	Baseline	Each evaluation
Nervous System Disorders	Peripheral motor neuropathy	X	X
Investigations	Creatinine increased	X	X
Respiratory, thoracic and mediastinal disorders	Pneumonitis	X	X
	Dyspnea	X	X

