13.0 Treatment/Follow-up Decision at Evaluation of Patient

- 13.1 Patients will be evaluated for response after 2 cycles of treatment. Patients who are NMR or PMD after 2 cycles of treatment will discontinue treatment and go to the event-monitoring phase per Section 18.0. Patients who are CMR or PMR will continue treatment per protocol.
- 13.2 Patients who develop progressive disease by either PET-CT based (PMD) or CT based (PD) response criteria (see Section 11.0) at any time while receiving therapy or during observation will go to the event-monitoring phase per Section 18.0.
- 13.3 Patients who go off protocol treatment for unacceptable adverse events, subsequent treatment or refusal will go to the event-monitoring phase per Section 18.0.
- 13.4 Observation: The patient will be observed every 30 days x90 days then every 90 days x 2.5 years, then every 6 months until 5 years from registration. If the patient develops disease progression (see section 13.2) or receives subsequent treatment before disease progression while in observation, they will go directly to the event monitoring phase per section 18.0.
- 13.5 Patients who achieve a PMR or CMR will receive a maximum total of 8 cycles of treatment. After 8 cycles, they go to observation per Section 13.4 above.
- 13.6 Early Safety Analysis Phase Only: If a patient fails to complete the first cycle (21 days) of treatment for reasons other than toxicity, the patient will be regarded as in evaluable and will be replaced.

- 13.7 A patient is deemed *ineligible* if after registration, it is determined that at the time of registration, the patient did not satisfy each and every eligibility criteria for study entry. The patient may continue treatment off-protocol at the discretion of the physician as long as there are no safety concerns, and the patient was properly registered. The patient will go directly to the event-monitoring phase of the study (or off study, if applicable).
- If the patient received treatment, all data up until the point of confirmation of ineligibility must be submitted. Event monitoring will be required per Section 18.0 of the protocol.
 - If the patient never received treatment, on-study material and the End of Active Treatment/Cancel Notification Form must be submitted. No further data submission is necessary.

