- 15.199b Assess patients medications. Patients who are taking medications that are CYP3A4 inhibitors (i.e ketoconazole) should be closely monitored for adverse reactions. Nivolumab side effects vary greatly from those of traditional chemotherapy and can vary in severity from mild to life threatening. Instruct patients to report any side effects to the study team immediately. Side effects may be immediate or delayed up to months after discontinuation of therapy. Most side effects are reversible with prompt intervention of corticosteroids. Additionally combination therapy (with ipilimumab) tends to have a higher rate of immune mediated side effects.
- 15.199c Monitor LFT's closely as elevations in these levels could indicate early onset autoimmune hepatitis. Patients should also be instructed to report any jaundice, or right upper quadrant pain to the study team immediately.
- 15.199g Endocrinopathies (including hypopituitarism, hypothyroidism, hypophysitis, new onset diabetes and adrenal insufficiency) are seen with this agent. Patients may present only with the vague sense of fatigue and "not feeling well". Additional symptoms may be that of nausea, sweating and decreased activity tolerance. Instruct patients to report these signs or symptoms immediately and obtain appropriate labs as ordered by MD.
- 15.199h Pancreatitis is possible with nivolumab. Instruct patients to report abdominal pain, nausea and vomiting to the study team.
- 15.199i Patients who are started on steroid therapy for any side effects of nivolumab toxicity should be instructed to take the steroids as ordered, and not to discontinue abruptly as symptoms may return and be severe. Patients may be on steroid therapy for weeks. Instruct patients to report

any increase or change in side effects with any dosage decrease as patients may need a slower taper.

- 15.199j Monitor renal function as patients may experience acute interstitial nephritis. Report any increase of levels to the study team.

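### Section 4.0 schedules no metabolic panel or TSH at observation visits, although Section 15 warns that nivolumab effects can appear months after treatment stops

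*Combined protocol and SAP*

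**What the plan says.** The table in Section 4.0 has five columns: baseline, before each new cycle, restaging (6 to 8 weeks after Day 1 of Cycle 8), early end of treatment, and observation. The row "Comprehensive metabolic panel: (ALT, AST, total bilirubin, alkaline phosphatase), BUN or serum urea level, creatinine", which also covers glucose, amylase and lipase, and the row "TSH (with Free T4 and Free T3" are marked in the first four columns and blank in the fifth. Adverse event assessment and CBC are marked in all five. INR is marked under observation with a footnote limiting it to clinical indication; the two blank rows carry no such mark. Footnote 11 places on-treatment thyroid tests at every third cycle, for patients receiving nivolumab.

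On the visits themselves, Section 13.4 says "The patient will be observed every 30 days x90 days then every 90 days x 2.5 years", and the column heading in Section 4.0 ends "then every 6 months until 5 years from registration) +/-14Days". Section 7.3 gives different later intervals but the same three 30-day visits. The note to Section 3.18 counts observation as part of Active Monitoring: "Phase of a study (i.e., active treatment and observation), participants must be willing to return to the consenting institution for follow-up".

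On the risk, the nursing guidelines in Section 15.19 state "Side effects may be immediate or delayed up to months after discontinuation of therapy", and Section 15.291 says much the same. Both lists ask staff to watch liver tests and renal function and describe endocrinopathy and pancreatitis. Neither sets a test date.

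On collection, Section 10.54 calls for "adverse events to be graded at each evaluation per the CTCAE v4.0 grading" and lists creatinine increased among its four terms. For events outside that list, Section 10.55 collects treatment-related Grade 2 events, all Grade 3 and 4 events, and deaths. On early stopping, Section 13.3 reads "Patients who go off protocol treatment for unacceptable adverse events, subsequent treatment or refusal will go to the event-monitoring phase per Section 18.0".

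**The concern.** The plan names a late risk that is partly visible only in blood tests, yet its last scheduled chemistry and thyroid test for a completer comes at restaging. Blood is still drawn for CBC at each observation visit and adverse events are still assessed there, but nothing schedules the tests that would show a silent rise in transaminases, creatinine, lipase or TSH.

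Safety and tolerability is a secondary objective (Section 2.22). Section 16.324 reports it as the maximum grade per event type in all eligible treated patients. A silent late event can therefore be missing from those tables, or be found later than it could have been. The absence of an event after restaging cannot be told apart from the absence of a test.

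**Working it through.** The plan gives no figure on this point, and no sample size or error rate depends on it. The check compares dates and counts tests.

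**1. Last scheduled test.** The last dose is on Cycle 8 Day 1 and restaging is 6 to 8 weeks later: 6 × 7 = 42 to 8 × 7 = 56 days after the last dose.

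**2. Observation visits without the tests.** This assumes no delay and no progression.
- Treatment lasts 7 × 21 + 42 to 56 = 189 to 203 days.
- Sections 4.0 and 13.4 then give 3 visits in 90 days, 10 in 2.5 years (913/90, rounded down), and 3 up to five years: (1826 − 1192 to 1206)/182.6, rounded down. The total is 16.
- Section 7.3 gives 3 + 180/60 + 8 + 3 = 17.
- Each visit has an adverse event assessment and a CBC; none has a scheduled panel or TSH. The proposed change concerns only the first three.

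**3. What the three 30-day visits would add.** The documents do not state the origin of the 90 days in so many words, so both readings are shown, in days after the last dose (±14-day window in brackets).

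| Origin | Visit 1 | Visit 2 | Visit 3 | Visit 3 past restaging |
|---|---|---|---|---|
| End of Cycle 8 (Section 13.5, with the 6–8 week Cycle 8 of Section 7.22) | 72–86 (58–100) | 102–116 (88–130) | 132–146 (118–160) | 90 (76–104) |
| Last dose (one reading of Section 7.3) | 30 (16–44) | 60 (46–74) | 90 (76–104) | 34–48 (20–62) |

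For the second row, 90 − 56 = 34 and 90 − 42 = 48; with the window, 76 − 56 = 20 and 104 − 42 = 62. The first reading fits better, because the second puts an observation visit inside Cycle 8.

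**4. Context from drug exposure.** Section 15.25 gives a half-life of about 27 days, so five half-lives are 5 × 27 = 135 days. Simple decay leaves 0.5^(42/27) = 0.34 to 0.5^(56/27) = 0.24 of the drug at restaging. Between 135 − 56 = 79 and 135 − 42 = 93 days of that window have no scheduled chemistry or thyroid test. Drug decay does not fix the timing of immune-mediated events, so this is only a scale.

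**5. Cost in tests.** Three per patient entering observation: 3 × 56 = 168 of each. With the 7 spare patients of Section 16.22 and no de-escalation, 56 + 7 = 63 and 3 × 63 = 189. The overall total of 75 (56 + 12 + 7) is not the right base. It is reached only with two de-escalation cohorts, and dose levels −1 and −2 in Section 7.11 both omit nivolumab.

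**6. Events that could be missed.** Such an event must be asymptomatic, visible only in the laboratory, and first arise after restaging. For terms outside the Section 10.54 list it must also be a related Grade 2 event or a Grade 3–4 event. The nivolumab percentages in Section 15.27 are overall frequencies, not late-event rates, and cannot be used to count such events.

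**The case against.** The strongest reply is that this is a judgement about how long to test well patients. The plan already schedules one post-treatment panel and TSH. After that, every observation visit has history, examination and adverse event assessment; Section 15 has laboratory tests ordered when endocrine symptoms are reported; and Section 10.53 collects serious events after dosing stops. The affected analysis is a set of descriptive frequency tables. All of this stands and keeps the point small. It does not supply the missing tests, and reliance on symptoms is weakest for endocrinopathy, which Section 15 says may show only as vague fatigue.

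A reader might infer that Section 10.54 contradicts Section 4.0 by requiring creatinine to be graded where none is drawn. The documents do not establish that. The evaluations in Section 10.54 are undefined, and Sections 7.3 and 7.6 use the word for the 21-day treatment visits. Grading can also use any result at hand. The mismatch exists only if observation visits count as evaluations, and then only for creatinine.

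A further fair objection is that patients who stop for toxicity go to event monitoring, so the change does not reach them and makes laboratory follow-up less equal across the pooled safety population. This stands and needs disclosure. Finally, Section 18, Appendix V and the Forms Packet were not in the text available, and any of them could add post-treatment tests.

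**Conclusion.** The point holds as a minor gap between the stated risk and the schedule. In the text available, a completer has no scheduled chemistry or thyroid test later than 42 to 56 days after the last dose, against a warning of effects delayed by months.

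The likely effect is late detection or some under-counting of the narrow class of events in step 6 of the working. Its size cannot be estimated, because the documents give no late-event rate. It would be wrong to conclude that late toxicity goes unmonitored or that the safety results would be invalid: symptomatic and serious events have other routes of capture. The primary endpoint and the efficacy decision rules in Sections 16.211 and 16.212 are unaffected.

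The conclusion assumes that the unseen sections do not schedule these tests. The gain from the change depends on the origin of the 90 days: 90 days of further scheduled testing if observation starts at the end of Cycle 8, 34 to 48 days if it starts at the last dose.

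**What to change.** In Section 4.0, mark the metabolic panel and TSH at the three observation visits held every 30 days for 90 days, for patients who received nivolumab (consistent with footnote 11), using the blood draw already made for the CBC. After that, test as clinically indicated. Leave grading under Section 10.54 unrestricted, so that any creatinine result is graded. Check Section 18 and Appendix V first for tests already required.

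In the safety report, and in Section 16.324 if it is amended, state that scheduled laboratory follow-up runs through the third 30-day visit only for patients who enter observation. For those sent to event monitoring under Sections 13.1 to 13.3, it ends at the end-of-treatment visit, or at restaging if they had already completed treatment.

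The cost is a test-schedule amendment and up to three extra panels and TSH tests per patient entering observation: at most 168 of each for 56 patients, or 189 for 63 without de-escalation. With de-escalation the number falls sharply, because later patients receive no nivolumab. No new visit or blood draw is needed. Reported laboratory event rates may rise slightly. If the 90 days run from the last dose, the day-30 visit precedes restaging and only two visits add later information.
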